10.2.1 Treatment-Emergent Adverse Events

Treatment-emergent AEs (TEAEs) are defined as any AE with the onset that is after the first dose of study drug. Events where the onset date is the same as the study drug start date are assumed to be treatment-emergent. All TEAEs will be summarized overall, as well as by primary MedDRA SOC and PT. The SOCs will be presented in alphabetical order, and the PTs will be presented in alphabetical order within each SOC.

The number and percentage of subjects experiencing treatment-emergent AEs will be summarized.

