Congenital Anomaly	An anomaly detected at or after birth, or any anomaly that results in fetal loss.
Persistent or Significant Disability/Incapacity	An event that results in a condition that substantially interferes with the activities of daily living of a study subject.

**Important Medical Event
Requiring Medical or Surgical
Intervention to Prevent
Serious Outcome**

An important medical event that may not be immediately life-threatening or result in death or hospitalization, but based on medical judgment may jeopardize the subject and may require medical or surgical intervention to prevent any of the outcomes listed above

All AEs reported from the time of study drug administration

 will be collected, whether solicited or spontaneously reported by the subject. In addition, study procedure-related serious and nonserious AEs will be collected from the time the subject signs the study-specific informed consent.

The following definitions will be used for serious adverse reaction (SAR) and suspected unexpected serious adverse reaction (SUSAR):

SAR	Defined as all noxious and unintended responses to an investigational medicinal product related to any dose administered that result in an SAE as defined above.
SUSAR	Refers to individual SAE case reports from clinical trials where a causal relationship between the SAE and the investigational medicinal product was suspected by either the sponsor or the investigator, is unexpected (not listed in the applicable Reference Safety Information), and meets one of the above serious criteria.

AbbVie will be responsible for SUSAR reporting for the investigational medicinal product in accordance with global and local requirements.

Adverse events will be monitored throughout the study to identify any of special interest that may indicate a trend or risk to subjects.

[REDACTED]
[REDACTED]
[REDACTED]
[REDACTED]
[REDACTED]
[REDACTED]

[REDACTED]
[REDACTED]
[REDACTED]

Upon identification and awareness of 1 or more of these events, the investigator must document and report the event by completing an AE eCRF, and must notify the AbbVie nonemergency contact and assigned clinical research associate by email or telephone call within 72 hours of awareness (if non-serious). The SAE form is not needed unless the AESI is serious. If the AESI meets SAE criteria (which are listed above), it must be reported per the sponsor's SAE reporting requirements described above [REDACTED].

Adverse Event Severity and Relationship to Study Drug

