7.5 Statistical Analyses for Safety

The safety analyses will be performed using the safety population. The safety parameters will include incidence of AEs and change from baseline in vital signs. [REDACTED]

Treatment-emergent AEs are defined as any AE with the onset that is after the first dose of study drug.

An overview of AEs will be presented consisting of the number and percentage of subjects experiencing at least one event for each of the following AE categories:

- Any TEAE
- Any TEAE related to study treatment according to the investigator
 - Any TEAE related to study procedure according to the investigator
 - Any TEAE related to study drug according to the investigator
- Any severe TEAE
- Any serious TEAE
- Any TEAE leading to death
- Any AESI

- Any PDSOT AE
- All deaths

Treatment-emergent AEs will be summarized by system organ class (SOC) and PT; by maximum relationship to study drug as assessed by the investigator (e.g., reasonable possibility or no reasonable possibility) and SOC and PT; by maximum severity and SOC and PT; and by subject number and SOC and PT. Specific TEAEs will be counted once for each subject for calculating percentages, unless stated otherwise. In addition, if the same AE occurs multiple times within a subject, the highest severity and level of relationship to investigational product will be reported.

Vital sign measurements will be summarized for changes from baseline at each assessment timepoint.

[figure not shown]

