10.2.2 Adverse Event Overview

An overview of AEs will be presented consisting of the number and percentage of subjects experiencing at least one event for each of the following AE categories:

- Any TEAE
- Any TEAE related to study treatment according to the investigator
 - Any TEAE related to study procedure according to the investigator
 - Any TEAE related to study drug according to the investigator
- Any mild TEAE
 - Any mild TEAE related to study treatment according to the investigator

- Any moderate TEAE
 - Any moderate TEAE related to study treatment according to the investigator
- Any severe TEAE
 - Any severe TEAE related to study treatment according to the investigator
- Any serious TEAE
 - Any serious TEAE related to study treatment according to the investigator
- Any TEAE leading to discontinuation
- Any treatment-emergent adverse event of special interest (AESI)
- Any possible distant spread of toxin (PDSOT) TEAE
- All deaths
- Any TEAE leading to death

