10.2.5 SAEs (Including Deaths) and Adverse Events Leading to Study Drug Discontinuation

Serious AEs (including deaths) and AEs leading to study drug discontinuation will be summarized by SOC and PT and in listing format.

10.2.6 Adverse Events of Special Interest and Possible Distant Spread of Toxin Adverse Events

Treatment-emergent adverse events of special interest (AESIs) will be summarized by PT.

Possible distant spread of toxin (PDSOT) TEAEs will be summarized by PT.

Tabular listings of AESIs and PDSOT TEAEs will be provided.

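### The TEAE definition rests on onset date alone, so an AE dated before Day 1 that worsens after the injection on the same record is outside the SAP's TEAE tables and its AESI and PDSOT summaries

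*SAP*

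**What the plan says.** SAP 10.2.1 gives the rule: "Treatment-emergent AEs (TEAEs) are defined as any AE with the onset that is after the first dose of study drug". Its next sentence settles ties on the dosing date: "Events where the onset date is the same as the study drug start date are assumed to be treatment-emergent". Protocol 7.5 has the same rule, "Treatment-emergent AEs are defined as any AE with the onset that is after the first dose of study drug", but not the tie-break. The sentence is complete in both documents; no redaction interrupts it. Neither the rule nor the AE definition in Protocol 6.1 mentions worsening of an event that is already present.

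On collection, Protocol 6.1 takes in all AEs reported from study drug administration onward (part of that sentence is blacked out). For the period before dosing it says that "study procedure-related serious and nonserious AEs will be collected from the time the subject signs the study-specific informed consent".

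On reporting, the SAP limits its special-interest outputs to treatment-emergent events. SAP 10.2.2 has an overview row for treatment-emergent AESIs and another reading "Any possible distant spread of toxin (PDSOT) TEAE". SAP 10.2.6 adds "Treatment-emergent adverse events of special interest (AESIs) will be summarized by PT" and "Possible distant spread of toxin (PDSOT) TEAEs will be summarized by PT". The overview in Protocol 7.5 lists AESIs and PDSOT events without that limit.

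**The concern.** A treatment-emergent flag should separate what was there before treatment from what appeared or got worse after it. A rule based only on onset date does the first part and half of the second. If an event started a few days before the injection, was mild, and became severe afterwards, and the site updates the existing record, the rule classes it as not treatment-emergent whatever its later course.

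For such records the omission runs one way: only post-injection deterioration is lost. The placebo arm does not offset it, because deterioration caused by the drug would fall in the BOTOX arm. Incidence of AEs is listed among the primary endpoints for both regions in the protocol synopsis, and PDSOT terms were identified prospectively (Protocol 6.1). In categories that rare, a single case is the difference between none and some.

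**Working it through.** The documents state no figure that depends on this definition, so there is nothing to reproduce. The check is a comparison of text, followed by simple arithmetic for scale.

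**Step 1. Can a record dated before Day 1 exist?** Yes. Procedure-related AEs are collected from consent, and the activity schedule (Protocol Appendix D) has AE assessment at screening, Day -14 to Day -7, and again on Day 1. After dosing, the visible collection wording turns on when an AE is reported, not on when it began.

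**Step 2. How does the rule sort AEs?**

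| AE | Status under SAP 10.2.1 |
|---|---|
| Onset after Day 1 | TEAE |
| Onset on Day 1, even before the injection | TEAE, by the tie-break sentence |
| Onset before Day 1, no change afterwards | Not a TEAE, as it should be |
| Onset before Day 1, worse after injection, entered as a new AE with its own onset date | TEAE |
| Onset before Day 1, worse after injection, original record and date kept | Not a TEAE: this is the gap |

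**Step 3. Does another rule repair the last row?** No. SAP 10.2 and 10.2.3 report the highest severity when the same AE occurs several times in a subject. That decides how an event is shown in a table; it does not make an earlier-onset record treatment-emergent. SAP 10.1 sets a pre-dose baseline for safety parameters analysed as change from baseline, such as vital signs, but nothing equivalent is stated for AE severity.

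**Step 4. Which outputs are affected?**

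| Output | Limited to treatment-emergent events? |
|---|---|
| SAP 10.2.3, by SOC and PT, severity and relationship | Yes |
| SAP 10.2.2, AESI and PDSOT overview rows | Yes |
| SAP 10.2.6, AESI and PDSOT summaries by PT | Yes |
| SAP 10.2.5, SAEs and AEs leading to study drug discontinuation | Not so worded |
| SAP 10.2.2, all deaths | Not so worded |
| Protocol 7.5, AESI and PDSOT overview rows | Not so worded |

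**Step 5. Scale.** The number of affected events cannot be derived from the documents. As an assumption, take 200 treated per arm, from the approximate arm sizes in SAP 2.4. One omitted subject is 1/200 = 0.5 percentage points.

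For exact two-sided 95% limits (Clopper-Pearson), the upper limit with 0 events is 1 − 0.025^(1/200) = 0.0183. With 1 event it solves (1 − p)^200 + 200p(1 − p)^199 = 0.025, which gives 0.0275. With 2 events it is 0.0357.

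| Events / 200 | Rate | Upper limit |
|---|---|---|
| 0 | 0.0% | 1.8% |
| 1 | 0.5% | 2.8% |
| 2 | 1.0% | 3.6% |

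These figures show what one or two missed cases would do. They do not estimate how many will be missed.

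**The case against.** The best case on the other side is that very little can fall through, for four reasons.

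- Only procedure-related AEs are collected before dosing, and the pre-dose activities visible in Appendix D (history, photography, a urine pregnancy test and the like) are non-invasive. The clearly exposed group is procedure-related AEs between consent and the day before Day 1. This stands, and it is why few events are expected.
- The AE definition in Protocol 6.1 is broad enough for a post-dose worsening to be an AE in its own right, with its own onset date. It would then already be a TEAE. This is possible, but the visible text does not say that sites record it so. The Operations Manual was not available and part of the collection sentence is blacked out. The classification should not depend on a data-entry convention that neither the protocol nor the SAP states.
- A serious worsening, or one leading to study drug discontinuation, would still be shown under SAP 10.2.5. This stands.
- For a PDSOT case to be lost, a listed term would have to exist as an AE record before Day 1, while the eligibility criteria exclude conditions that might interfere with neuromuscular function. This makes the loss unlikely, not impossible.

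A reader might also infer that headache or muscle soreness, named in Protocol 2.2 as reported complications, would be lost if already present at Day 1. The documents do not support that. Onset on Day 1 counts. An earlier complaint unrelated to study procedures would usually be medical history, with no pre-dose AE record whose date could be kept; a reported worsening would then most naturally be entered as a post-dose AE.

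**Conclusion.** The point holds in a narrow form. Both documents classify by onset alone, and no visible text brings in post-dose worsening. An AE record dated before Day 1 that worsens or becomes serious after the injection, with its date unchanged, is outside the SAP's TEAE tables and its AESI and PDSOT summaries.

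This rests on two conditions: that such a record exists, and that the worsening is not entered as a new AE. The expected number is small and cannot be computed from the documents. The 0.5 points per subject assumes 200 treated per arm, and it matters mainly where counts are near zero.

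Two stronger readings are tempting. One is that any event present before injection that worsens disappears from every safety table. The tie-break for Day 1, the SAE and discontinuation summaries and the protocol's unrestricted AESI and PDSOT rows all contradict it. The other is that the whole definition errs towards understating risk. It does so for the records described here, but the tie-break also counts Day 1 events that began before the injection, so the definition as a whole does not err in one direction.

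This is a cheap improvement to an otherwise workable rule, not a flaw that endangers the safety evaluation.

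**What to change.** In SAP 10.2.1, and in Protocol 7.5 at the next amendment, define a TEAE along these lines: *any AE with onset on or after the date of first dose of study drug, or any AE with earlier onset that increases in severity or becomes serious on or after that date.* This also brings the Day 1 rule into the protocol.

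Say how it will be implemented. If dated severity changes are captured, derive the flag from them. The visible text does not show that they are; if they are not, instruct sites to record such worsening as a new AE with its own onset date, and say so in the SAP. Because a specific AE is counted once per subject, the extra record does not inflate the percentages.

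Use the same flag for AESI and PDSOT, and reconcile the SAP's treatment-emergent AESI and PDSOT rows with the protocol's unrestricted ones.

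The cost is one sentence in each document plus either a derived flag or a data-entry instruction. The TEAE count may rise by a few events. No efficacy analysis or visit changes.

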10.2.2 Adverse Event Overview

An overview of AEs will be presented consisting of the number and percentage of subjects experiencing at least one event for each of the following AE categories:

- Any TEAE
- Any TEAE related to study treatment according to the investigator
 - Any TEAE related to study procedure according to the investigator
 - Any TEAE related to study drug according to the investigator
- Any mild TEAE
 - Any mild TEAE related to study treatment according to the investigator

- Any moderate TEAE
 - Any moderate TEAE related to study treatment according to the investigator
- Any severe TEAE
 - Any severe TEAE related to study treatment according to the investigator
- Any serious TEAE
 - Any serious TEAE related to study treatment according to the investigator
- Any TEAE leading to discontinuation
- Any treatment-emergent adverse event of special interest (AESI)
- Any possible distant spread of toxin (PDSOT) TEAE
- All deaths
- Any TEAE leading to death

10.2.3 Treatment-Emergent Adverse Events by SOC and/or PT

TEAEs will be summarized by SOC and PT; by maximum relationship to study drug as assessed by the investigator (e.g., reasonable possibility or no reasonable possibility) and SOC and PT; by maximum severity and SOC and PT; and by subject number and SOC and PT. Specific adverse events will be counted once for each subject for calculating percentages, unless stated otherwise. In addition, if the same adverse event occurs multiple times within a subject, the highest severity and level of relationship to study drug will be reported.

In addition, TEAEs will be summarized by PT and sorted by decreasing frequency for the total active group.

10.2.4 Treatment-Emergent Adverse Events per Patient-Years of Exposure

Not applicable.

10.2.5 SAEs (Including Deaths) and Adverse Events Leading to Study Drug Discontinuation

Serious AEs (including deaths) and AEs leading to study drug discontinuation will be summarized by SOC and PT and in listing format.

10.2.6 Adverse Events of Special Interest and Possible Distant Spread of Toxin Adverse Events

Treatment-emergent adverse events of special interest (AESIs) will be summarized by PT.

Possible distant spread of toxin (PDSOT) TEAEs will be summarized by PT.

Tabular listings of AESIs and PDSOT TEAEs will be provided.

10.3 Analysis of Laboratory Data

Not applicable.

10.4 Analysis of Vital Signs

Vital sign measurements of systolic and diastolic blood pressure, pulse rate, and respiratory rate, and changes from baseline at each assessment timepoint will be summarized by treatment group. In addition, potentially clinically important vital sign values will be summarized for systolic and diastolic blood pressure, pulse rate and temperature.

Table 3. Criteria for Potentially Clinically Important Vital Sign Values

Parameter	Flag	Criteria^a	
		Observed Value	Change From Baseline
Sitting systolic blood pressure, mm Hg	High		
	Low		
Sitting diastolic blood pressure, mm Hg	High		
	Low		
Heart rate, bpm	High		
	Low		
Temperature, degrees C	High		
	Low		

bpm = beats per minute; C = Celsius

a. Except for temperature, a postbaseline value is considered potentially clinically important if it meets both the observed-value and the change-from-baseline criteria; for temperature, only the observed-value criterion is needed to be potentially clinically important.

10.5 Safety Subgroup Analyses

Safety analyses for the summary of overall AEs will be performed by subgroups of sex, age group [REDACTED] race [REDACTED] ethnicity [REDACTED]
[REDACTED] and region [REDACTED]

10.6 Other Safety Analyses

Not applicable.

11.0 Other Analyses

Not applicable.

12.0 Interim Analyses

No interim analysis is planned for this study.

12.1 Data Monitoring Committee

No data monitoring committee (DMC) will be used for this study.

13.0 Overall Type-I Error Control

To control the family-wise Type I error rate at 0.05 for multiplicity across the primary and secondary analyses [REDACTED]

Thus, the hierarchical testing order follows for US FDA:

1. Primary composite: Achievement of Grade 1 or 2 (Minimal or Mild) and at least a 2-grade improvement from baseline based on both investigator's assessment using the C-APPS and subject's self-assessment using P-APPS at maximum contraction at Day 14
2. Secondary: Responses of *Satisfied* or *Very satisfied* on the ANLFQ: Satisfaction (Follow-up) Item 5 (effect of treatment) at Day 14
3. Secondary: Responses of *Not at all bothered* or *A little bothered* on the BAS-PP Item 2 (jawline) at Day 14
4. Secondary: Responses of *Not at all bothered* or *A little bothered* on the BAS-PP Item 1 (vertical neck bands) at Day 14

5. Secondary: Change from baseline on the ANLFQ: Impacts summary score at Day 14

The hierarchical testing order follows for EU regulatory agencies:

1. Coprimary: Achievement of at least a 2-grade improvement from baseline based on the following:
 - Investigator's assessment using C-APPS at maximum contraction at Day 14
 - Subject's self-assessment using P-APPS at maximum contraction at Day 14
2. Secondary: Achievement of a rating of Minimal or Mild according to subject's self-assessment using P-APPS at maximum contraction at Day 14
3. Secondary: Responses of *Satisfied* or *Very satisfied* on the ANLFQ: Satisfaction (Follow-up) Item 5 (effect of treatment) at Day 14
4. Secondary: Responses of *Not at all bothered* or *A little bothered* on the BAS-PP Item 2 (jawline) at Day 14
5. Secondary: Responses of *Not at all bothered* or *A little bothered* on the BAS-PP Item 1 (vertical neck bands) at Day 14
6. Secondary: Change from baseline on the ANLFQ: Impacts summary score at Day 14
7. Secondary: Change from baseline on the ANLFQ: Impacts summary score at Days 30, 60, and 90

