7.7 Overall Type I Error Control

Analyses will be conducted using a gated hierarchical testing procedure to preserve a familywise Type I error rate of $\alpha = 0.05$.

To control the family-wise Type I error rate at 0.05 for multiplicity across the primary and secondary analyses, a hierarchical testing strategy ²³ will be used.

Nominal p-values will then be provided.

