Hypothetical estimand for secondary continuous endpoints [REDACTED]	Change from baseline on the ANLFQ: Impacts summary score at Days 30, 60, and 90	Subjects who discontinue study prior to applicable timepoints or who do not have Day 30, 60, and 90 ANLFQ: Impacts summary score will be included in the analysis as a hypothetical scenario in which the assessments were conducted as per protocol	Mean change from baseline and mean differences between BOTOX and placebo treatment groups; analysis of variance [REDACTED]
Hypothetical estimand for secondary categorical endpoint [REDACTED]	Achievement of at least a 1-grade improvement from baseline based on the investigator's assessment using C-APPS at maximum contraction over time*	Subjects who discontinue study or who do not have C-APPS assessments will be included in the analysis as a hypothetical scenario in which the assessments were conducted as per protocol	Response rates and rate differences between BOTOX and placebo treatment groups; CMH test [REDACTED]
Hypothetical estimand for secondary categorical endpoint [REDACTED]	Achievement of at least a 1-grade improvement from baseline based on the subject's self-assessment using P-APPS at maximum contraction over time*	Subjects who discontinue study or who do not have P-APPS assessments will be included in the analysis as a hypothetical scenario in which the assessments were conducted as per protocol	Response rates and rate differences between BOTOX and placebo treatment groups; CMH test [REDACTED]

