9.0 Efficacy Analyses

9.1 General Considerations

Efficacy analyses for primary and secondary endpoints will be conducted in the ITT Population for the US and the mITT Population for the EU regulatory agencies. All other efficacy analyses will be conducted using the ITT population.

Analyses will be performed using a gated hierarchical testing procedure to preserve a family-wise Type I error rate of $\alpha = 0.05$.

To control the family-wise Type I error rate at 0.05 for multiplicity across the primary and secondary endpoints, a hierarchical testing strategy¹ will be used. For the US, the secondary endpoints assessed "over time" (see Section 3.2) will be excluded from the hierarchical testing strategy. [REDACTED]

[REDACTED] Nominal p-values will be provided thereafter.

The final analysis will be performed after all ongoing subjects have completed the study and the database has been locked. This will be the only analysis for the primary composite, coprimary and secondary efficacy endpoints, as well as all other efficacy endpoints.

Unless otherwise specified, categorical variables will be analyzed using Cochran-Mantel-Haenszel (CMH) test, [REDACTED]. Continuous variables will

be analyzed using analysis of covariance (ANCOVA) [REDACTED]
[REDACTED]

Unless otherwise specified, any subject who is randomized based on a wrong stratum will be analyzed according to the subject's actual stratum.

"Baseline" refers to the last non-missing observation before the first administration of study drug or randomization if no study drug is given. The change from baseline values will be computed as the post-baseline value minus the baseline value.

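### Does the last EU step, which puts Days 30, 60 and 90 on one line, leave the family-wise error rate open?

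*SAP*

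**What the plan says.** SAP 9.1 states the aim: "To control the family-wise Type I error rate at 0.05 for multiplicity across the primary and secondary endpoints". The same section and Protocol 7.7 call the procedure gated and hierarchical.

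SAP 13.0 turns this into two numbered lists, one per region. In the EU list, step 1 is a pair of endpoints labelled coprimary. Steps 2 to 6 hold one Day 14 comparison each; the two BAS-PP items have separate steps, and ANLFQ: Impacts at Day 14 is step 6. The list closes with "7. Secondary: Change from baseline on the ANLFQ: Impacts summary score at Days 30, 60, and 90".

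SAP Table 2 (section 2.1) treats "Change from baseline on the ANLFQ: Impacts summary score at Days 30, 60, and 90" as one estimand row, summarised as "Mean change from baseline and mean differences between BOTOX and placebo treatment groups". What is visible of that row does not say how the three days combine.

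For the US only, SAP 9.1 says that the endpoints assessed over time "will be excluded from the hierarchical testing strategy". No matching exclusion is visible for the EU.

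Part of the rule text is blacked out. In SAP 13.0 the blackout falls directly before "Thus, the hierarchical testing order follows for US FDA". In SAP 9.1 it falls directly before "Nominal p-values will be provided thereafter". Protocol 7.7 has "Nominal p-values will then be provided" with nothing visible for it to follow from.

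**The concern.** A fixed-sequence procedure controls error because each step is one test, or one joint test, at the full 0.05. Step 7 is the only step that names several comparisons under a plain secondary label. Step 1 also holds more than one, but its coprimary label tells the reader that both must succeed.

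Three readings of step 7 are possible:

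- test Day 30, then 60, then 90, and stop at the first failure;
- require all three days;
- test each day at 0.05 once step 6 passes.

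The third would allow any single day to be claimed and would exceed 0.05. The reading also decides which claim can be made. If only Day 30 were significant, it would be a controlled claim under the first and third readings and no claim under the second. If only Day 90 were significant, it would be a controlled claim under the third reading alone.

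**Working it through.** **Inputs.** Family-wise level 0.05 (SAP 9.1 and 13.0). Two-sided tests at 0.05, so the critical value is c = 1.96; Protocol 7.4 states this for the primary endpoint and I carry it to step 7. Three comparisons in step 7 (SAP 13.0). The correlation ρ between the Day 30, 60 and 90 test statistics is not in the documents; I assume it equal for each pair and take it from 0 to 0.9. I also assume step 6 passes with near certainty, which is the worst case for step 7.

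**The plan's own figure.** Read the coprimary pair as both-must-win and steps 2 to 6 as single tests at 0.05, each reached only after the previous success. A false claim then requires rejecting the first true null in the sequence, which has probability at most 0.05. The stated 0.05 therefore reproduces through step 6.

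**Step 7, each day at 0.05 on its own.** With k true nulls and ρ = 0, P(at least one false positive) = 1 − 0.95^k. For k = 3 this is 1 − 0.8574 = 0.1426; for k = 2 it is 1 − 0.9025 = 0.0975; for k = 1 it is 0.05. For any ρ the upper bound with k = 3 is 3 × 0.05 = 0.15. For ρ > 0, with Φ and φ the standard normal distribution and density functions:

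P = 1 − ∫ [Φ((c − √ρ f)/√(1 − ρ)) − Φ((−c − √ρ f)/√(1 − ρ))]^k φ(f) df

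| ρ | three nulls | two nulls (Days 60, 90) | one null (Day 90) |
|---|---|---|---|
| 0 | 0.1426 | 0.0975 | 0.05 |
| 0.3 | 0.1362 | 0.0951 | 0.05 |
| 0.5 | 0.1254 | 0.0907 | 0.05 |
| 0.7 | 0.1092 | 0.0835 | 0.05 |
| 0.8 | 0.0982 | 0.0781 | 0.05 |
| 0.9 | 0.0836 | 0.0704 | 0.05 |

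**Step 7, printed order.** A false claim requires rejecting the first true null among Days 30, 60 and 90, so the rate is at most 0.05 whichever days are null.

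**Step 7, all three required.** A false claim requires rejecting every true null, so the rate is at most 0.05. With three nulls true it is 0.0001 at ρ = 0 (0.05³ = 0.000125) and about 0.023 at ρ = 0.9.

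**Step 7, alpha split.** At 0.05/3 = 0.0167 per day the bound is 3 × 0.0167 = 0.05. The value at ρ = 0 is 1 − (1 − 0.0167)³ = 0.0492. Holm's procedure also holds 0.05.

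**What a fixed order costs.** Suppose power of 95%, 90% and 80% at Days 30, 60 and 90 (assumed). Tested alone, Day 90 is claimed with probability 80%. In fixed order at ρ = 0 this is 0.95 × 0.90 × 0.80 = 0.684; at ρ = 0.5, 0.7 and 0.9 it is 0.74, 0.76 and 0.79. With 80% power at every day, it is 0.80³ = 0.512 at ρ = 0, rising to 0.72 at ρ = 0.9. No single valid rule is therefore best on every count, and the choice among them is a trade-off.

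**Reading the texts together.** Protocol 7.7 and SAP 9.1 promise a gated procedure at 0.05 across primary and secondary endpoints. Three ungated tests at 0.05 inside one step would break both parts of that promise. The other readings break neither.

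**The case for a change.** The strongest case for a change is that the list itself shows no blackout in step 7 and is the place where the order is set out. Where the SAP wants an order it numbers the steps, even for two items of one questionnaire. The printed sequence of days suggests testing in order; the word joining them, and the single estimand row, suggest a joint test. These two natural readings lead to different claims, a rule chosen after unblinding would be open to criticism, and one line of wording would settle it.

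Much of this stands. The step 7 line is ambiguous as printed, and no visible text resolves it. It does not follow that error control is at risk. The list is introduced as the consequence of text that the public copy blacks out, so the sponsor's analysts may already have the rule. If they do not, the stated family-wise commitment steers them to a rule that holds 0.05.

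The upper figure of 14.3% also needs an unlikely setting: uncorrelated repeated scores in the same subjects, and no effect at Day 30 in a trial that has already passed every earlier step, including the same score at Day 14. If the effect has gone only by Day 90, there is no inflation at all.

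**Conclusion.** No change to the plan is called for. This is a detail that analysts can fill in line with the plan's stated error control, and the plan may already fill it in text withheld from the public copy.

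Any inflation arises only if each day is tested at 0.05 with no further gate: 8.4% to 14.3% with three true nulls, 7.0% to 9.8% with two, none with one, over assumed correlations from 0.9 down to 0. That reading contradicts the visible commitment to gated testing at 0.05. Under the printed order, an all-days rule, an equal split or Holm, the rate stays at or below 0.05.

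The reach is narrow: only claims about ANLFQ: Impacts at Days 30, 60 and 90 in the EU analysis depend on the reading.

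This conclusion rests on the blacked-out text not expressly allowing each day to be claimed separately at 0.05, and on whichever rule applies being settled before unblinding.
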